13.4. DISTRIBUTION OF QRS BY VISIT

The QRS values collected for each subject will be presented as summary statistics by visit and overall. They will also be presented by means of a Box Plot.

The number and percentage of subjects with the following categories for QRS parameters will be presented:

- i. QRS \leqslant 100 ms
- ii. $100 < QRS \leqslant 120$ ms
- iii. QRS > 120 ms

LEVEA – Statistical Analysis Plan

This analysis will be based on EP.

13.5. DISTRIBUTION OF THE LV PACING THRESHOLD MEASURED PER LV PACING VECTOR IN “IN-CLINIC LVAT” ALGORITHM

The possible LV pacing thresholds measured by each LV pacing vector at each LV pacing configuration are: 0.25, 0.50, 0.75, 1.00, 1.25, 1.50, 1.75, 2.00, 2.25, 2.50, 3.00, 3.5, 4.00, 4.50, 5.00 .

A frequency distribution of the categories $\leq 2.5V$, $2.5V - \leq 3.5V$, $3.5V - \leq 5V$, $> 5V$, and a Histogram will be plotted by configuration and visit.

For the LV tests performed for subjects with either IS1 and IS4 leads six LV vectors common to IS1 and IS4), the percentage will be calculated based on the number of subjects implanted with either IS1 and IS4 leads.

For the LV tests performed for subjects with IS4 leads (eight LV vectors pertaining only to IS4), the percentage will be calculated based on the number of subjects implanted with IS4 lead.

This analysis will be based on ITT.

13.6. DISTRIBUTION OF THE LV IMPEDANCE PER VISIT

The possible LV impedance measured is between 200 and 3000 Ohms at M0 and M1 visit.

Summary Statistics of LV impedance measured will be presented by visit and overall. A Box-plot of the same will also be plotted.

This analysis will be based on EP.

14. SAFETY ANALYSIS

Adverse events definitions are derived from ISO 14155:2011 - Clinical investigation of medical devices for human subjects.

14.1. GENERAL RULES FOR AE REPORTING

Adverse events that occurred after the inclusion visit and prior to study termination or Lost-to follow-up will be presented for all subjects in the Safety Population.

If there are less than 10 Adverse events reported in the study, the Adverse Events will be reported only by listing.

The following Safety Events will be reported in the study based on their time of occurrence:

During initial testing procedure

- All adverse events e.g. procedural complications (serious and non-serious), excluding direct and clinically expected physiologic effects of testing

Throughout the study

- All Serious cardiovascular and access site Adverse Events
- All deaths

LEVEA – Statistical Analysis Plan

- Unanticipated (Serious) Adverse Device Effect
- Device Deficiencies (including but not limited to failures, malfunctions, and product nonconformities) with or without associated adverse events

The classification of AEs for statistical analysis will be based on site-reported events for the final diagnosis in the Safety populations.

A positive relationship (YES) will include those assessed as related or unknown if related to the device/procedure. A negative relationship (NO) will be limited to those assessed as not being related to the device/procedure.

The adverse events (AEs) in the Safety population will be assessed using descriptive statistics by

- Diagnosis (AE Category, AE Term, AE clarifiers)
- Relationship – (Yes/No)
- Device Interrogation (Yes/No)
- Treatment and Medication
- Outcome (Resolved/Death/Pending)
- Relationship: to procedure, to device
- Expectedness for ADE (Yes/No)

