8.5.2. Secondary and ancillary endpoints

Secondary and ancillary endpoints will be assessed at all follow-ups using descriptive statistics. Point estimates and 95% CI will be presented wherever possible.

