8.6. SAFETY ANALYSIS

The secondary objective of assessing safety and device deficiencies of the compound will be answered by summarizing the relevant endpoints by means of descriptive statistics on the Safety population.

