10. SECONDARY EFFICACY ANALYSES

Secondary and Ancillary endpoints will be assessed at all visits using descriptive statistics. Point estimates and exact CI (Clopper & Pearson, 1934) will be presented wherever possible.

Whenever a Statistical test is performed for a Secondary Endpoint, it is of hypothesis generating and descriptive in nature.

10.1. ASSESSMENT OF DIAGNOSTIC ACCURACY OF “IN-CLINIC LVAT” TEST AT M0 VISIT: INDEPENDENT REVIEWER VALIDATION OF LV THRESHOLD VALUE PROVIDED BY ALGORITHM

This endpoint is the number of accurate determination of the LV pacing threshold value provided by the algorithm feature and an independent reviewer, on all LV pacing vectors and all pacing configurations available at M0 visit.

Diagnostic accuracy is defined as an accurate adjudication by an independent reviewer of LV threshold value provided by the algorithm. The adjudication is based on capture and loss of capture analysis on electrogram strips recorded and stored during “In-Clinic LVAT” tests. The LV threshold value provided by the algorithm compared to the reviewer adjudication is considered accurate if the difference is within ± 1 step (meaning ± 0.25 V if threshold < 2.5V, else ± 0.5 V as measured). The definition of an Accurate LV threshold value is provided above in Table 5.

In case the algorithm and the reviewer adjudication provide both a LV threshold value equal to “>5V” (the LV vector test has resulted in “no capture” or “threshold value higher than 5V at starting amplitude), the LV threshold value is considered accurate. Number and percentages of “accurate” and “inaccurate” matches will be presented along with the exact 95% CI (Clopper & Pearson, 1934).

This analysis will be performed on M0-ITT population.

Decomposition of Diagnostic Accuracy by LV Vector and by LV pacing configuration

Total number of attempted, completed, and accurate LV vector tests will be presented by LV vector for each LV pacing configuration.

For the LV tests performed for subjects with either IS1 and IS4 leads (six LV vectors common to IS1 and IS4), the percentage for the number of LV vector tests “attempted”, will be calculated based on the number subjects implanted with either IS1 and IS4 leads.

For the LV tests performed for patients with IS4 leads (eight LV vectors pertaining only to IS4), the percentage for the number of LV vector tests “attempted”, will be calculated based on the number of patients implanted with IS4 lead.

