11. SECONDARY SAFETY ANALYSES

11.1. ASSESSMENT OF THE DEVICE CHARACTERISTICS IN TERMS OF SAFETY AND DEVICE DEFICIENCY

- A. Serious adverse device events and device deficiencies will be collected during each subject visit. Confirmation of absence of USADE during “In-Clinic LVAT” tests will be evaluated by analyzing all SAEs and device deficiencies (DD) collected at each visit.

This secondary endpoint will be based on IP.

- B. Algorithm characteristic: Underestimated Assessments

Assessment of LV pacing threshold underestimation: comparison to manual LV threshold value will be performed by comparing manual and automatic LV threshold values at each visit. An underestimated LV threshold value of “In-Clinic LVAT” feature is defined as a value result more than 2 steps below the LV threshold measured manually (meaning -0.5V if threshold<2.5V, else -1V as measured) . Please see table 6.

LEVEA – Statistical Analysis Plan

Number and percentages of “underestimated” assessments will be presented along with the exact 95% CI (Clopper & Pearson, 1934) by M0 and M1 visit. Only subjects with non-missing manual data will be considered.

The reasons for LV pacing threshold underestimation at M0 visit will be presented as table and listing. The missing reasons (if any) for underestimation will be presented as “Not available”. For the table, the number and percentages of the reasons will be presented with the denominator of the percentages based on the total number of LV pacing threshold underestimated.

Total number of attempted, completed,, Underestimated LV vector tests will be presented by LV vector for each LV pacing configuration by visit.

For the LV tests performed for patients with either IS1 and IS4 leads (six LV vectors common to IS1 and IS4) , the percentage for the number of LV vector tests “attempted”, will be calculated based on the number of patients implanted with either IS1 and IS4 leads.

For the LV tests performed for patients with IS4 leads (eight LV vectors pertaining only to IS4), the percentage for the number of LV vector tests “attempted”, will be calculated based on the number of patients implanted with IS4 lead.

For number of LV vector tests “completed”, the percentage will be calculated based on the number of LV vector tests attempted.

For number of LV vector tests “Underestimated”, the percentage calculated based on number of Complete LV vector tests .

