14.2. ANALYSIS OF ADVERSE EVENTS

The following AE summaries will be produced for all subjects in Safety set:

Overall Summary of AEs, ADEs, Device Deficiencies, SAEs and Deaths will be provided for number of subjects with at least one event and number of events

- Any AEs
 - Expected
 - Unexpected
 - Was Device Interrogation performed (Yes/No)
 - Related to procedure (Yes/No)
 - Related to device (Yes/No)
 - Outcome (Resolved/Death/Pending)
- Any ADEs
 - Expected
 - Unexpected
 - Was Device Interrogation performed (Yes/No)
- Any Device Deficiencies
 - Expected
 - Unexpected

LEVEA – Statistical Analysis Plan

- Issue resulted in any (serious) adverse event(Yes/No)
- Was reprogramming done (Yes/No)
- Device re-intervention (Yes/No)
- Device returned to Sorin (Yes/No)
- Subject discontinued from the study following the DD(Yes/No)
- Serious adverse events (SAEs)
- SAE (Other than Death)
- SAE Leading to Death
- Deaths
- Device related
 - ✓ Unexpected Serious Adverse Device Effect (SADE)
 - ✓ Expected SADE
- Procedure related
- Not device or procedure relationship
- Device related ISO (procedure and/or device related)
 - Unexpected Serious Adverse Device Effect (SADE)
 - Expected SADE

For the following -

- AEs
- ADEs
- Device deficiencies
- SAEs

events leading to Hospitalization will be analysed with the following details:

- Hospitalization required (Yes/No)
- Duration of Hospitalization (Summary statistics – Mean, SD, Q1, Median, Q3, Min, Max)
- Did it cause Permanent Disability/incapacity (Yes/no)
- Intervention to Prevent Life Threatening Injury or Permanent Damage (yes/No)
- Life Threatening Illness or Injury (Yes/No)

For the following -

- AEs
- ADEs

LEVEA – Statistical Analysis Plan

- Device deficiencies
- SAEs

events requiring treatment or medication will be analysed to provide the following:

- Treatment provided (Yes/No)
- Device programming required (Yes/No)
- Device re-intervention required (Yes/No)
- Any other intervention required (Yes/No)
- Led to change in cardiovascular medication since last visit (Yes/No)

For the following -

- AEs
- ADEs
- Device deficiencies
- SAEs

Outcome will be reported. Outcome can be any of the following:

- Final outcome pending
- Final outcome
- Resolved
- Death
- On-going or chronic
- Unknown

The following information for Device deficiencies will be summarized:

- Component involved (obtained from Device deficiency page of eCRF)
- Device Deficiency category (obtained from Device deficiency page of eCRF)

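### With fewer than 10 adverse events the SAP gives a listing and no AE-type rates, and the USADE endpoint has no rate or confidence limit although 0 of 59 still allows up to 6.1%

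*SAP*

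**What the plan says.** Safety and device deficiencies form the last secondary objective (Protocol 3.2; SAP 2.1.2). The plan treats them in several places.

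- Protocol 8.6: the objective "will be answered by summarizing the relevant endpoints by means of descriptive statistics on the Safety population". No minimum number of events is set.
- Protocol 8.5.2, on secondary and ancillary endpoints: "Point estimates and 95% CI will be presented wherever possible". SAP 10 says much the same: "Point estimates and exact CI (Clopper & Pearson, 1934) will be presented wherever possible".
- SAP 14.1: "If there are less than 10 Adverse events reported in the study, the Adverse Events will be reported only by listing".
- SAP 14.2: "The following AE summaries will be produced for all subjects in Safety set". A long list of counts and breakdowns follows, with no condition stated there. It ends by sending every event to a listing.
- SAP 11.1 A, repeating Protocol 4.1.3 e: "Confirmation of absence of USADE during" the automatic tests is to be evaluated from the SAEs and device deficiencies collected. Item A gives no percentage, interval or criterion. Its analysis set is the Included Population: "This secondary endpoint will be based on IP".
- SAP 11.1 B, under the same objective, is fuller: "Number and percentages of “underestimated” assessments will be presented along with the exact 95% CI (Clopper & Pearson, 1934) by M0 and M1 visit". SAP 11.1 C gives numbers and percentages of tests with unexpected function.

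SAP 3.1 records no change in analysis from the protocol.

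**The concern.** When events are few, the uncertainty is most of the safety result. A listing shows what happened but not the rate, and not the range of rates still compatible with the data. If nothing happened, SAP 17.1 reduces the listing to a single line saying there are no qualifying data.

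Wording that seeks to confirm an absence adds to this. A report that follows the plan could set an empty listing beside a statement that absence was confirmed, and never state the upper limit. The feature is not CE-marked, so that limit is what a reader deciding on its use would want. Items B and C of the same SAP section do report percentages, and B an exact interval. Item A, the one about serious device effects, has neither.

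**Working it through.** **1. The plan's own figures.** The documents state no precision for any safety rate. The only size figure is the one for the primary endpoint (SAP 2.3): null rate 90%, expected rate 95%, one-sided alpha 2.5%, power 80%. Treating tests as independent, as the plan does, an exact binomial test with n = 231 rejects at 217 or more successes, with attained alpha 0.0239 and power 81.6%. Then 231/5 = 46.2, rounded up to 47, and 47/(1 − 0.20) = 58.75, rounded up to 59. All three figures reproduce. I use 59 as the safety denominator, assuming every enrolled subject counts.

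**2. What zero USADEs would show.** With no events in n subjects, the exact upper limit is 1 − 0.025^(1/n) for a two-sided 95% interval and 1 − 0.05^(1/n) for a one-sided 95% limit.

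- n = 59: 1 − 0.025^(1/59) = 6.1% two-sided; 1 − 0.05^(1/59) = 4.95% one-sided.
- If only 47 subjects contributed, the limits would be 7.5% and 6.2%.

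The chance of seeing no event in 59 subjects is (1 − p)^59: 55% at a true rate of 1%, 30% at 2% and 17% at 3%. To exclude a rate of 1% with zero events, at one-sided 95%, takes ln(0.05)/ln(0.99), rounded up to 299 subjects.

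**3. What the listing rule can leave without a rate.** The largest count under the rule is nine. If each event falls in a different subject, the crude rate is 9/59 = 15.3%. The Clopper-Pearson limits are the 2.5% quantile of Beta(9, 51), 7.2%, and the 97.5% quantile of Beta(10, 50), 27.0%. A single event, 1/59 = 1.7%, has limits 0.04% and 9.1%. Both intervals can be computed, as can the one for zero, so the qualifier in Protocol 8.5.2 and SAP 10 does not excuse leaving them out.

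**4. How often the rule would apply.** The documents give no expected AE rate, so this is an assumption shown as a range. With at most one event per subject, P(fewer than 10 events) is the binomial probability P(X ≤ 9) with n = 59:

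| Assumed AE rate per subject | P(listing only) |
|---|---|
| 10% | 93% |
| 15% | 61% |
| 20% | 23% |

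The answer depends almost wholly on the assumed rate.

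**5. The denominator.** SAP 14 reports AEs on a Safety population. Protocol 8.2 defines one, but SAP section 6 does not, and the disposition list in SAP 7.1 omits it. SAP 11.1 A uses the Included Population. The entry criteria require an implanted study device, so the two sets should nearly coincide, but the SAP does not say that they do.

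**The case against.** The case for leaving the text alone has real substance.

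- **Not the whole objective.** A reader might infer that the safety objective can end with no rate at all. It cannot: items B and C of SAP 11.1 keep their percentages whatever the AE count. The rule names adverse events, and SAP 14.1 lists device deficiencies as a separate kind of safety event, so nothing says that the deficiency summaries are dropped. This stands. The loss is limited to AE-type rates.
- **Not a flat contradiction.** SAP 14.1 is headed as general rules, so 14.2 can be read as subject to it. Protocol section 8 asks only for relevant major changes to be declared, and a display rule for small counts is arguably not one. This stands too. The fair statement is that 14.1 is not reconciled with 14.2 or with Protocol 8.6.
- **Not a planned inference.** A reader might take 11.1 A as a plan to conclude that the risk is absent. The sentence concerns events during the tests and carries no hypothesis or criterion. It also calls itself a secondary endpoint, so the general interval statement in SAP 10 may already reach it. But SAP 10 is headed efficacy, 11.1 A names no interval, and the wording still invites more than the data can give.
- **Not hidden.** Every event is listed and population sizes are tabulated, so a crude rate can be worked out by hand. That is true, and it limits the harm. It does not supply the interval or settle the denominator, and it is not the summary that Protocol 8.6 describes.
- **Not shown to be likely.** AE collection is narrow and follow-up short, which makes a low count plausible. Without an expected rate the documents do not support calling it likely.

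**Conclusion.** The point holds in a narrow form. A stated rule can remove the AE-type rates and their uncertainty from a stated secondary objective, and the USADE endpoint is worded as a confirmation with no rate or limit. Under the rule, up to 15.3% of subjects with an event could be reported without a percentage. A result of no USADE would be compatible with a true per-subject rate of up to 6.1% (two-sided 95%) or 4.95% (one-sided 95%).

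These sizes assume 59 subjects in the denominator and, for the 15.3%, one event per subject. Fewer subjects would widen the limits. The severity is minor: the primary endpoint is unaffected and the raw events remain visible.

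**What to change.** 1. In SAP 14.1, confine the fewer-than-10 rule to the detailed breakdowns, such as AE term, treatment and outcome.
2. Whatever the count, report for AE, ADE, SAE, SADE, USADE and device deficiency how many subjects had one or more, the percentage and the exact 95% CI. Include rows with zero. State in SAP 14.2 that this table is always produced.
3. In Protocol 4.1.3 e and SAP 11.1 A, replace the confirmation wording with: *observed number and per-subject rate of USADE during the tests, with exact 95% upper limit*. State the sidedness. The upper end of the two-sided interval would match the Clopper-Pearson intervals used elsewhere in the SAP.
4. Define the Safety population in SAP section 6, add it to the disposition list, and use one denominator for SAP 11.1 A and section 14.

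The cost is one short table from data already collected. The safety statement will also sound less favourable: with no events it would read *no USADE observed in 59 subjects, upper limit 6.1%*.

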14.2. ANALYSIS OF ADVERSE EVENTS

The following AE summaries will be produced for all subjects in Safety set:

Overall Summary of AEs, ADEs, Device Deficiencies, SAEs and Deaths will be provided for number of subjects with at least one event and number of events

- Any AEs
 - Expected
 - Unexpected
 - Was Device Interrogation performed (Yes/No)
 - Related to procedure (Yes/No)
 - Related to device (Yes/No)
 - Outcome (Resolved/Death/Pending)
- Any ADEs
 - Expected
 - Unexpected
 - Was Device Interrogation performed (Yes/No)
- Any Device Deficiencies
 - Expected
 - Unexpected

LEVEA – Statistical Analysis Plan

- Issue resulted in any (serious) adverse event(Yes/No)
- Was reprogramming done (Yes/No)
- Device re-intervention (Yes/No)
- Device returned to Sorin (Yes/No)
- Subject discontinued from the study following the DD(Yes/No)
- Serious adverse events (SAEs)
- SAE (Other than Death)
- SAE Leading to Death
- Deaths
- Device related
 - ✓ Unexpected Serious Adverse Device Effect (SADE)
 - ✓ Expected SADE
- Procedure related
- Not device or procedure relationship
- Device related ISO (procedure and/or device related)
 - Unexpected Serious Adverse Device Effect (SADE)
 - Expected SADE

For the following -

- AEs
- ADEs
- Device deficiencies
- SAEs

events leading to Hospitalization will be analysed with the following details:

- Hospitalization required (Yes/No)
- Duration of Hospitalization (Summary statistics – Mean, SD, Q1, Median, Q3, Min, Max)
- Did it cause Permanent Disability/incapacity (Yes/no)
- Intervention to Prevent Life Threatening Injury or Permanent Damage (yes/No)
- Life Threatening Illness or Injury (Yes/No)

For the following -

- AEs
- ADEs

LEVEA – Statistical Analysis Plan

- Device deficiencies
- SAEs

events requiring treatment or medication will be analysed to provide the following:

- Treatment provided (Yes/No)
- Device programming required (Yes/No)
- Device re-intervention required (Yes/No)
- Any other intervention required (Yes/No)
- Led to change in cardiovascular medication since last visit (Yes/No)

For the following -

- AEs
- ADEs
- Device deficiencies
- SAEs

Outcome will be reported. Outcome can be any of the following:

- Final outcome pending
- Final outcome
- Resolved
- Death
- On-going or chronic
- Unknown

The following information for Device deficiencies will be summarized:

- Component involved (obtained from Device deficiency page of eCRF)
- Device Deficiency category (obtained from Device deficiency page of eCRF)
- Resulted in AE (obtained from Device deficiency page of eCRF)
- Resulted in SAE

All AEs, ADEs, Device Deficiencies, SAEs and Deaths will be listed.

15. ABBREVIATIONS

ADE	Adverse Device Effect
AE	Adverse Event
CA	Competent Authority

LEVEA – Statistical Analysis Plan

CI	Confidence Interval
CIP	Clinical Investigation Plan
CRT	Cardiac Resynchronization Therapy
CRT-D	Cardiac Resynchronization Therapy on a defibrillator
DD	Device Deficiency
DF1	Standard for connection of defibrillator leads described in the ISO 11318:2002
DF4	Standard for connection of RV tachy leads described in the ISO 27186
DMP	Data Management Plan
EC	Ethic Committee
ECG	Electrocardiogram
eCRF	Electronic Case Report Form
EGM	Electrogram
ESC	European Society of Cardiology
GCP	Good clinical practice
ICD	Implantable Cardioverter Defibrillator
IFU	Instruction For Use
In-Clinic LVAT	In-clinic Left Ventricular Auto-Threshold
IRB	Institutional Review Board
IS1	Standard for connection of pacing/sensing leads described in the ISO 5841-3:2013
IS4	Standard for connection of LV CRT leads described in the ISO 27186
ITT	Intention To Treat
LV	Left Ventricle
LVCM	Left Ventricular Capture Management
LVAT	Left Ventricular Auto Threshold

LEVEA – Statistical Analysis Plan

M0-ITT	M0- Intention To Treat
M1-ITT	M1- Intention To Treat
PI	Principal Investigator
PNS	Phrenic Nerve Stimulation
RF	Radiofrequency
RTD / DTR	Real-Time Data
RV	Right Ventricle
RVAT	Right Ventricular Auto Threshold
SADE	Serious Adverse Device Effect
SAE	Serious Adverse Event
SAP	Statistical Analysis Plan
SPOT	Spatial Projection of Tachycardia
USADE	Unanticipated Serious Adverse Device Effect

16. REFERENCES

17. APPENDICES 1: ANALYSIS SPECIFICATION

17.1. GENERAL PRINCIPLES

The statistical analysis will be performed on the analysis study database with appropriate software, SAS® Software version 9.4 or above (SAS Institute, Cary, N.C.).

Where a listing or table has been planned, but no data meet the criteria, then a single line stating 'No data meeting the criteria are present' will be provided in the output.

All the data collected and derived in the trial will be presented in subject data listings.

LEVEA – Statistical Analysis Plan

